5.2.4.2. Part B (q1wk dosing) and Part C (Arm 3; q1wk dosing)

In the event of an AE or lab criteria that prevents dosing of LV (see Section 5.2.3.1), the LV dose for the week should be withheld. LV may be resumed when the dosing criteria are met. If a dose(s) of LV is withheld, the corresponding visit may be skipped and resume the following week (eg, if the Day 8 dose is skipped, visits will resume on Day 15; if Day 8 and Day 15 doses are skipped, visits will resume on Day 1 of the following cycle). Day 1 of a cycle may be delayed but not skipped.

Dose reduction of LV may be considered in the event of recurrent AE despite withheld doses. Dose re-escalation following dose reduction is not allowed. Dose levels for LV dose reductions in Part B and Part C (Arm 3) are shown in [Table 11](#).

For Part C (Arm 3), subjects who discontinue pembrolizumab due to a pembrolizumab-related AE (see Section 5.3.4) may continue LV. Similarly, subjects who discontinue LV for a LV-related AE may continue pembrolizumab. See Section 5.5.3 for details on managing overlapping AEs.

Table 11: Q1wk LV dose reductions

Starting Dose	First Dose Reduction (mg/kg/wk)	Second Dose Reduction (mg/kg/wk)
Starting dose 1.0 mg/kg/wk	0.75	0.5
Starting dose 1.25 mg/kg/wk	1.0	0.75

For nonclinical events requiring alteration in dosing schedule (eg, holidays, scheduling conflicts), a +2 day dosing window is allowed. Nonclinical events that require skipping a dose(s), must be approved by sponsor medical monitor. At least 7 days must elapse between each administration of LV.

Dose modification guidelines for LV q1wk treatment-associated toxicity are detailed in [Table 12](#).

Table 12: Dose modifications for LV treatment-associated toxicity (Part B and Part C [Arm 3] q1wk dosing)

Toxicity	Grade 1	Grade 2	Grade 3	Grade 4
Peripheral neuropathy ^a	Continue at same dose level	Withhold until toxicity resolves to \leq Grade 1; treatment may resume at the next lower dose level (see Table 11)	Withhold until toxicity resolves to \leq Grade 1, then resume treatment at the next lower dose level (see Table 11)	Discontinue treatment
Hyperglycemia		Hold for blood glucose >250 mg/dL or >13.9 mmol/L. Resume treatment once elevated blood glucose has improved to ≤ 250 mg/dL or ≤ 13.9 mmol/L and subject is clinically and metabolically stable (see Section 5.6 for details).		
Non-hematologic ^a (except peripheral neuropathy and hyperglycemia)	Continue at same dose level	Continue at same dose level	Withhold dose until toxicity is \leq Grade 2 or has returned to baseline, then resume treatment at same dose level ^b	Withhold dose until toxicity is \leq Grade 2 or has returned to baseline, then reduce dose to the next lower dose level (see Table 11) and resume treatment, or discontinue at the discretion of the investigator ^{b,c}
Hematologic ^a	Continue at same dose level	Continue at same dose level	Withhold until toxicity resolves to \leq Grade 2 or baseline ^{d,e} , then resume treatment at the same dose level. If the dose is held >48 hours, the dose may be omitted and dosing may resume on the next scheduled dosing day. See Sections 5.4.2 and 5.4.3 on allowed concomitant therapy and myeloid growth factors.	Withhold until toxicity resolves to \leq Grade 2 or baseline ^{d,e} , then reduce dose to the next lower dose level (see Table 11) if treatment is resumed ^{b,c} . If the dose is held >48 hours, the dose may be omitted and dosing may resume on the next scheduled dosing day. If Grade 4 neutropenia recurs, reduce dose to the next lower dose level (see Table 11) if treatment is resumed, or discontinue at the discretion of the investigator. See Sections 5.4.2 and 5.4.3 on allowed concomitant therapy and myeloid growth factors.
Febrile neutropenia ^a	Not applicable	Not applicable	Withhold until febrile neutropenia resolves and neutrophil count returns to \leq Grade 2 or baseline and then resume treatment at the next lower dose level (see Table 11). If the dose is held >48 hours, the dose may be omitted and dosing may resume on the next scheduled dosing day. If febrile neutropenia recurs, reduce dose to the next lower dose level (see Table 11) if treatment is resumed, or discontinue at the discretion of the investigator. See Sections 5.4.2 and 5.4.3 on allowed concomitant therapy and myeloid growth factors.	

The maximum dose will be 200 mg per infusion for subjects enrolled in Part B and Part C (Arm 3).

- a Only 2 dose reductions are allowed without prior medical monitor approval. Additional toxicities should be managed with dose delays. Medical monitor approval is needed for further dose reduction.
- b Subjects who develop Grade 3 or 4 electrolyte laboratory abnormalities may continue study treatment without interruption if a management plan consistent with institutional practice and regular monitoring are put in place.
- c Treatment should be discontinued for subjects who experience Grade 4 infusion-related reactions.
- d Support with blood product transfusions allowed per institutional standard of care.
- e Subjects who develop Grade 3 or 4 lymphopenia may continue study treatment without interruption.

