- Assess progression-free survival (PFS) in subjects who respond to LV as monotherapy (Part A, Part B, and Part C Arm 1 [Cohort 8 only]) and LV + pembrolizumab (Part C Arms 2 and 3, Cohort 8 only) as measured by RECIST v1.1 for all tumors, and by investigator-determined PSA for prostate cancer
- Assess survival as measured by overall survival (OS) in subjects who respond to LV as monotherapy (Part A, Part B, and Part C Arm 1 [Cohort 8 only]) and LV + pembrolizumab (Part C Arms 2 and 3, Cohort 8 only)
- Assess pharmacokinetics (PK) and immunogenicity of LV (Parts A-C)

Additional

- Assess biomarkers of biological activity, resistance, and predictive biomarkers of response

Study Population

Adult subjects with the following advanced solid tumors (Parts A, B, and C):

- Cohort 1: small cell lung cancer (SCLC) (Parts A and B)
- Cohort 2: non-small cell lung cancer-squamous (NSCLC-squamous) (Parts A and B)
- Cohort 3: non-small cell lung cancer–nonsquamous (NSCLC-nonsquamous) (Parts A and B)

- Cohort 4: head and neck squamous cell carcinoma (HNSCC) (Parts A and B)
- Cohort 5: esophageal squamous cell carcinoma (esophageal-squamous) (Parts A and B)
- Cohort 6: gastric and gastroesophageal junction (GEJ) adenocarcinoma (Parts A and B)
- Cohort 7: castration-resistant prostate cancer (CRPC) (Part B only)
- Cohort 8: melanoma (Parts B and C)

Number of Planned Subjects

Up to approximately 414 subjects will be enrolled in the entire study, including up to 72 subjects in Part A (LV 2.5 mg/kg on Day 1 of every 21-day cycle [q3wk] dosing), up to 252 subjects in Part B (LV Day 1, Day 8, and Day 15 every 21-day cycle [q1wk] dosing), and approximately 90 subjects in Part C ([Cohort 8 melanoma only] LV 1.5 mg/kg Day 1 and Day 8 but not Day 15 every 21-day cycle [2q3wk], LV 1.5 mg/kg 2q3wk + 200 mg pembrolizumab q3wk, LV 1.25 mg/kg q1wk + 200 mg pembrolizumab q3wk).

Study Design

This global, open-label, multicenter trial is designed to assess the activity, safety, and tolerability of LV monotherapy for the treatment of solid tumors. The study consists of 3 Parts evaluating subjects in 8 tumor cohorts, summarized in the table below.

- **Part A:** LV administered by intravenous (IV) infusion at a dose of 2.5 mg/kg on Day 1 of each 21-day cycle (q3wk).
- **Part B:** LV administered by IV infusion at a dose of 1.0 mg/kg (Cohort 1 through Cohort 6) or 1.25 mg/kg (Cohort 1 through Cohort 8) on Day 1, Day 8, and Day 15 of each 21-day cycle (q1wk).

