c Includes subjects enrolled prior to and after the safety analysis at a selected LV dose.

d Includes subjects enrolled prior to and after the interim analysis for futility at a selected LV dose and schedule.

e Part C for Cohort 8 will start enrollment upon completion of enrollment for Cohort 8 Part B.

Interim analysis for futility will be performed separately for each cohort of Part A and Part B after approximately 12 efficacy-evaluable subjects of a given cohort have been treated at a specific LV dose and schedule (details in Section 9.3.9).

For Part C, randomization will be stratified according to BRAF mutational status (wild-type vs mutated).

Figure 3: Study Schema Overview

Subjects will be enrolled in Part A until the individual tumor cohorts have 12 subjects or activation of Protocol Amendment 1 at each respective investigative site, whichever comes first. Upon activation of Protocol Amendment 1 at each investigative site, all subsequent subjects enrolled at that site will be in Part B. Subjects in Part A may cross over to Part B with sponsor's approval based on emerging safety and efficacy data.

Part B will assess LV q1wk in the tumor cohorts. The planned dose levels in Part B are shown in [Table 8](#). Initially, approximately 12 subjects across the tumor cohorts will be enrolled and receive LV 1.0 mg/kg q1wk. Based on collective safety data from the initial 12 subjects and from the concurrently ongoing phase 1 study SGNLVA-001 evaluating LV q1wk in breast cancer, subsequent enrollment in Part B will either:

- Continue enrolling up to 12 subjects in each tumor cohort at LV 1.0 mg/kg q1wk for interim analysis for futility, or
- Enroll an additional 12 subjects across the tumor cohorts to receive LV 1.25 mg/kg q1wk (Dose Level +1) for safety analysis. If tolerability is demonstrated, enrollment will continue to 12 subjects in each tumor cohort at LV 1.25 mg/kg q1wk for interim analysis for futility.
- Intrapatient dose escalation to a dose level shown to be safe is permitted with sponsor approval if a subject tolerates study treatment.

Table 8: Planned dose levels for Part B (LV q1wk dosing)

Dose Level	Weekly LV Dose (mg/kg/wk)	Maximum LV Dose in a 21-Day Cycle (mg/kg/cycle)
0	1.0	3.0
+1	1.25	3.75

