5.2.3.1. Dosing Criteria

The following laboratory criteria must be met on Day 1 of each cycle prior to LV administration:

- Neutrophil count $\geq 1000/\mu\text{L}$ (\leq Grade 2)
- Aspartate aminotransferase \leq Grade 2
- ALT \leq Grade 2
- Total bilirubin \leq Grade 2

In Part B and C, neutrophil count must be $\geq 1000/\mu\text{L}$ (\leq Grade 2) prior to LV administration on Day 8 and Day 15 (if receiving q1wk dosing) of each cycle.

If the above criteria are not met on the day of dosing, hold the LV dose until the criteria are met. In addition, hold LV dosing for subjects with \geq Grade 2 peripheral neuropathy (see Table 10).

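### For q1wk dosing, three Table 12 cells permit a dose held over 48 hours to be omitted, with no exception for Day 1, while the Section 5.2.4.2 text forbids skipping Day 1

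*Protocol*

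**What the plan says.** All the q1wk passages apply to the same subjects: Part B and Part C Arm 3.

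- **Protocol 5.2.3.1 (Dosing Criteria).** This sets the laboratory thresholds, including neutrophils of at least 1000/µL on each dosing day, and then says "If the above criteria are not met on the day of dosing, hold the LV dose until the criteria are met".
- **Protocol 5.2.4.2, text.** It refers back to 5.2.3.1 for the trigger. When dosing is prevented, "the LV dose for the week should be withheld", and "the corresponding visit may be skipped and resume the following week". The worked examples are Day 8 alone, or Day 8 and Day 15 together. The paragraph closes with "Day 1 of a cycle may be delayed but not skipped". A separate sentence adds "At least 7 days must elapse between each administration of LV".
- **Protocol 5.2.4.2, Table 12.** For Grade 3 hematologic toxicity, Grade 4 hematologic toxicity and febrile neutropenia: "If the dose is held >48 hours, the dose may be omitted and dosing may resume on the next scheduled dosing day". The sentence names no dosing day and makes no exception. It does not appear in the neuropathy, hyperglycemia or other non-hematologic rows.

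No statement says whether the text or the table takes precedence.

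**The concern.** A Grade 3 or 4 neutrophil count on Day 1 fails the 5.2.3.1 criterion, brings in the 5.2.4.2 text and falls in the hematologic row of Table 12. If it has not recovered after 48 hours, the table permits the dose to be dropped with the calendar kept, whereas the text permits only a later start to the cycle.

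Consistent dose conduct and exposure reporting are at stake. Cycle counts, dose per cycle and the tabulation of modifications would depend on which passage a site followed. The dose-modification types named in Protocol 9.3.8.1 and SAP 6.4 are delay, reduction and unplanned adjustment. None is an omission, so one event could be classified in different ways. In Arm 3, pembrolizumab is given on Day 1, about 60 to 90 minutes after LV, and its timing is unclear if the Day 1 LV dose is omitted. Part B has up to 252 subjects and Arm 3 has 30, so the rule covers up to 282 of about 414 planned.

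A secondary point concerns Day 8 and Day 15. The text withholds the week's dose with no 48-hour threshold. By setting that threshold, Table 12 implies that a dose can still be given after a shorter hold.

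**Working it through.** **Inputs.** Three weekly doses per 21-day cycle; planned cycle totals from Table 8 (Protocol 3.1); first reductions from Table 11 (1.25 to 1.0 and 1.0 to 0.75 mg/kg); the seven-day minimum interval from 5.2.4.2. The length of a Day 1 hold is not given. I assume 3 and 7 days, and show 14 days as well because 5.2.4.2 sets no maximum delay.

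**Reproducing the plan's figure.** 3 × 1.0 = 3.0 and 3 × 1.25 = 3.75 mg/kg per cycle. Both match Table 8.

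**Cycle total: Day 1 held more than 48 hours, resolved by the scheduled Day 8.** The text gives three delayed doses, because the seven-day interval moves Day 8 and Day 15 as well. The table allows two doses, Day 8 and Day 15.

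| Start (mg/kg) | Toxicity | Dose after hold (mg/kg) | Text: 3 doses (mg/kg) | Table: 2 doses (mg/kg) |
|---|---|---|---|---|
| 1.25 | Grade 3 hematologic | 1.25 | 3.75 | 2.5 |
| 1.25 | Grade 4 hematologic or febrile neutropenia | 1.0 | 3.0 | 2.0 |
| 1.0 | Grade 3 hematologic | 1.0 | 3.0 | 2.0 |
| 1.0 | Grade 4 hematologic or febrile neutropenia | 0.75 | 2.25 | 1.5 |

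The two-dose total is one third lower in every row.

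**Weekly dose intensity at 1.25 mg/kg, no reduction.** Intensity = cycle total ÷ weeks; percent of planned = intensity ÷ 1.25.

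- Omitted: 2.5 ÷ 3 = 0.833 mg/kg/week, 66.7%.
- 3-day delay: 3.75 ÷ (24/7) = 1.094, 87.5%.
- 7-day delay: 3.75 ÷ (28/7) = 0.938, 75.0%.
- 14-day delay: 3.75 ÷ (35/7) = 0.750, 60.0%.

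Against the fixed two-dose figure, the gap narrows and then changes sign as the delay lengthens.

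**Two cautions on that comparison.** First, the 14-day line lies outside the condition of recovery by Day 8. If the hold itself lasted 14 days, the table could permit Day 8 to be omitted too, leaving one dose. Second, weekly dosing has no rest week. Count the planned Day 1 as calendar day 1. After a 7-day hold, the text gives infusions on days 8, 15, 22 and 29. The table gives days 8 and 15, then the next cycle on days 22 and 29. The infusion dates are the same and only the cycle labels differ. After a 3-day hold, the text gives days 4, 11, 18 and 25, and the table gives days 8, 15, 22 and 29, four days later. The per-cycle difference therefore partly reflects where the cycle boundary falls.

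**Side by side.** On Day 1, omission is permitted by the table and forbidden by the text. On Day 8 or Day 15 after a hold of 48 hours or less, the table implies the dose can be given. The text withholds the week's dose but also says LV may be resumed once the criteria are met, without saying whether that can be in the same week.

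**The case against.** The strongest reply is that the table is permissive and the Day 1 sentence is a specific prohibition in the same section. A site that always delays Day 1, and omits only Day 8 or Day 15, complies with both. That is correct, and it keeps this a matter of reconciling wording. It does not remove the conflict, because the documents do not state that order of precedence and a site that omits Day 1 is following the toxicity-specific table as written.

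For Day 8 and Day 15, Section 6.3.3 and Appendix C give a +2 day dosing window, which equals 48 hours and might explain the threshold. Section 5.2.4.2, however, ties that window to nonclinical events. This part is an ambiguity and not a contradiction.

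A reader might infer more than the documents support:

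- **That any held dose may be omitted.** The 48-hour sentence stands in three cells only.
- **That there are three rival hold rules.** Section 5.2.3.1 is the trigger that the 5.2.4.2 text elaborates.
- **That subjects lose a third of their LV exposure.** One third is a single-cycle total, and the weekly rate behaves differently, as shown above.
- **That the problem is frequent.** In SGNLVA-001 q1wk (N=81), Grade 3 or higher neutropenia was 21.0% and neutrophil count decrease 11.1%. These are incidences over all treatment in breast cancer, their overlap is not stated, and they do not count Day 1 holds beyond 48 hours.
- **That one reading allows dosing during Grade 3 or 4 neutropenia.** Section 5.2.3.1 requires at least 1000/µL before each weekly dose under either reading.

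**Conclusion.** The point holds for q1wk dosing and for the three named Table 12 cells: the table permits, for Day 1, what the text of the same section forbids. Where a Day 1 hold exceeds 48 hours and resolves by the scheduled Day 8, the result is three delayed doses or two. In that cycle this is 3.75 against 2.5 mg/kg at 1.25 mg/kg without reduction, and 3.0 against 2.0 mg/kg after the first reduction from 1.25 mg/kg.

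No single figure or direction can be claimed for weekly dose intensity, because it depends on the length of the delay, which is assumed here. The number of subjects affected cannot be estimated from the documents. The confirmed ORR analysis, which uses all treated subjects, and the sample size are unaffected. Dose conduct, per-cycle exposure, cycle counts and dose-modification summaries are affected.

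**What to change.** Reconcile the Section 5.2.4.2 text and the three Table 12 cells, consistently with 5.2.3.1, so that they state one rule on two questions: whether the 48-hour omission applies to Day 1, and whether a Day 8 or Day 15 dose may be given late in the same week. The clinical choice is the sponsor's, and none is proposed here. The same edit should make clear what happens to Arm 3 pembrolizumab under whichever rule is kept. The exposure summaries in Protocol 9.3.8.1 and SAP 6.4 should say how an omitted dose is classified.

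The cost is wording in one section and one table, plus a line in the exposure summaries. No procedures, visits or subjects are added.

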5.2.4.3. Part C (Arm 1 and Arm 2; 2q3wk dosing)

In the event of an AE or lab criterion that prevents dosing of LV (see Section 7.6.1), the LV dose should be withheld until the dosing criteria are met. If the Day 1 dose is held, the Day 8 dose should not be given until 7 days later.

In the event of an AE or lab criterion that prevents dosing of LV on Day 8 during the cycle (see Section 7.6.1), the LV dose for the week may be withheld up to 4 days for Arm 1 and Arm 2. LV may be resumed when the dosing criteria are met. If a dose of LV is withheld for more than 4 days, the corresponding visit may be skipped and dosing resumed at the following visit (eg, if the Day 8 dose is skipped, visits will resume on Day 1 of the following cycle). Day 1 of a cycle may be delayed but not skipped.

Dose reduction of LV may be considered in the event of recurrent AE despite withheld doses. Dose re-escalation following dose reduction is not allowed. Dose levels for LV dose reductions in Part C (Arms 1 and 2) are shown in [Table 13](#) .

For Arm 2, subjects who discontinue pembrolizumab due to a pembrolizumab-related AE (see Section 5.3.4) may continue LV. Similarly, subjects who discontinue LV for a LV-related AE may continue pembrolizumab. See Section 5.5.3 for details on managing overlapping AEs.

Dose modification guidelines for LV 2q3wk treatment-associated toxicity are described in [Table 13](#) (Arm 1 and Arm 2).

Table 13: 2q3wk LV dose levels

Starting dose	First dose reduction	Second dose reduction ^a
1.5 mg/kg	1.25 mg/kg	1.0 mg/kg ^b

^a If patients have more than 2 dose reductions (with medical monitor approval), dose will be the next appropriate reduced dose level determined by discussion between investigator and medical monitor.

^b The dose may be reduced to 0.75 mg/kg following approval from the medical monitor.

For nonclinical events requiring alteration in dosing schedule (eg, holidays, scheduling conflicts), a +4-day dosing window is allowed. If more than a +4-day window is needed, the medical monitor must be consulted. The medical monitor must approve skipped dose(s) for nonclinical events. At least 7 days must elapse between administrations of LV.

[Table 14](#) describes dose modifications for LV treatment-associated toxicity for the 2q3wk schedule (Arm 1 and Arm 2).

Doses reduced for LV-related toxicity should not be re-escalated.

If a subject has a clinically significant, unresolved AE on Day 1 of C2 or beyond, the start of the cycle may be delayed for up to 14 days. Delays of >14 days must be approved by the medical monitor.

In the event a subject is unable to tolerate their dose level, additional treatment cycles (C2 or later) may be administered at a lower dose level upon approval by the medical monitor.

Table 14: Dose modifications for LV-associated toxicity (Part C [Arms 1 and 2]; 2q3wk dosing)

Toxicity	Grade 1	Grade 2	Grade 3	Grade 4
Peripheral neuropathy ^a	Continue at same dose level	Withhold until toxicity resolves to \leq Grade 1; then resume treatment at the next lower dose level (see Table 13)	Withhold until toxicity resolves to \leq Grade 1, then resume treatment at the next lower dose level (see Table 13)	Discontinue treatment
Hyperglycemia			Hold for blood glucose >250 mg/dL or >13.9 mmol/L. Resume treatment once elevated blood glucose has improved to ≤ 250 mg/dL or ≤ 13.9 mmol/L and subject is clinically and metabolically stable (see Section 5.6 for detail).	
Non-hematologic ^a (except peripheral neuropathy and hyperglycemia)	Continue at same dose level	Continue at same dose level	Withhold dose until toxicity is \leq Grade 2 or has returned to baseline, then resume treatment at same dose level ^b	Withhold dose until toxicity is \leq Grade 2 or has returned to baseline, then reduce dose to the next lower dose level (see Table 13) and resume treatment, or discontinue at the discretion of the investigator ^{b,c}
Hematologic ^a	Continue at same dose level	Continue at same dose level	Withhold until toxicity resolves to \leq Grade 2 or baseline ^{d,e} . For neutropenia, strongly consider G-CSF support , then resume treatment at the same dose level. Prophylactic G-CSF support should be strongly considered for subsequent cycles. (See Appendix G)	Withhold until toxicity resolves to \leq Grade 2 or baseline ^{d,e} . For neutropenia, strongly consider G-CSF support , then resume treatment at the same dose level. Prophylactic G-CSF support is required for all subsequent cycles. If Grade 4 neutropenia recurs despite G-CSF support, consider dose reduction to dose level -1 (see Table 13) or discontinuation. (Appendix G)
Febrile neutropenia ^a			G-CSF support is required for treatment of febrile neutropenia. Withhold until febrile neutropenia resolves and neutrophil count returns to \leq Grade 2 or baseline then resume treatment at the same dose level. Prophylactic G-CSF is required for all subsequent cycles. If febrile neutropenia recurs despite G-CSF factor support, consider dose reduction to dose level -1 (see Table 13) or discontinuation.	

The maximum dose will be 200 mg per infusion for patients enrolled in Part C.

a Only 2 dose reductions are allowed without prior medical monitor approval. Additional toxicities should be managed with dose delays. Medical monitor approval is needed for further dose reduction.

b Subjects who develop Grade 3 or 4 electrolyte laboratory abnormalities may continue study treatment without interruption if a management plan consistent with institutional practice and regular monitoring are put in place.

c Treatment should be discontinued for subjects who experience Grade 4 infusion-related reactions.

d Support with blood product transfusions allowed per institutional standard of care.

e Subjects who develop Grade 3 or 4 lymphopenia may continue study treatment without interruption.

